#### **Table 16-4 Renal Event Follow Up**

# **FOLLOW-UP OF RENAL EVENTS**

- Urine dipstick and sediment microscopy evidence of DIN: crystals, red blood cells (dysmorphic/glomerular vs. non-dysmorphic/non-glomerular), white blood cells, tubular epithelial cells
- Blood pressure and body weight
- Serum creatinine, BUN, electrolytes (sodium, potassium, phosphate, calcium), bicarbonate and uric acid
- Urine output

Review and record possible contributing factors to the renal event (co-medications, other co-morbid conditions) and additional diagnostic procedures (MRI etc.) in the CRF

- Event resolution: (sCr within 10% of baseline or PCR < 1 g/g Cr, or ACR <300 mg/g Cr) or
- Event stabilization: sCr level with ±10% variability over last 6 months or protein-creatinine ratio stabilization at a new level with ±50% variability over last 6 months.
- Analysis of urine markers in samples collected over the course of the DIN event

	7.1 Variables					
	7.2	Descrip	tive analyses			
		1	Commercially Confidential Inform			

Novartis	Confidential	Page 4 of 20
SAP Amendment 1		Study No. CQBW251B2202
List of tables		
Table 1-1	Objectives and related endpoints	6
Figure 1-1	Study design	8
Table 4-1	Protocol deviation codes and analysis sets	9
Table 8-1	Biomarkers to be fully reported in CSR	

List of abbreviations

AE	Adverse Event
b.i.d.	twice a day
CASA-Q	Cough and Sputum Assessment Questionnaire
CAT	COPD Assessment Test
CFU	Colony Forming Units
COPD	Chronic Obstructive Pulmonary Disease
CRF	Case Report Form
CSP	Clinical Study Protocol
CSR	Clinical Study Report
CV	coefficient of variation
DMS	Document Management System
eCRF	Electronic Case Report Form
EQ-5D-3L	Euro Quality of Life-5 Dimensions-3 Level
FEV1	Forced expiratory volume in 1 second
FVC	Forced vital capacity
GOLD	Global Initiative for Chronic Obstructive Lung Disease
HRCT	High Resolution Computed Tomography
IA	Interim Analyses
ICS	Inhaled Corticosteroids
LABA	Long-Acting
LAMA	Long-Acting Muscarinic Antagonists
LLOQ	Lower limit of quantification
MedDRA	Medical Dictionary for Drug Regulatory Affairs
PD	Pharmacodynamics
PK	Pharmacokinetics
PT	Preferred Term
RAP	Reporting & Analysis Process
SAE	Serious Adverse Event
SAP	Statistical Analysis Plan
SAS	Statistical Analysis System
SD	Standard deviation
SE	Standard error
SOC	System Organ Class
TFLs	Tables, Figures, Listings
ULOQ	Upper limit of quantification
WHO	World Health Organization

1 Introduction

1.1 Scope of document

The RAP documents contain detailed information to aid the production of Statistics & Programming input into the Clinical Study Report (CSR) for trial "*CQBW251B2202*".

The Statistical analysis plan (SAP) describes the implementation of the statistical analysis planned in the protocol.

1.2 Study reference documentation

- 1. Clinical Study Protocol version 02 dated 25-Aug-2021
- 2. eCRF version 3.0 dated 03-Jul-2020.

1.3 Study objectives

Table 1-1	Objectives and related endpoints
-----------	----------------------------------

Objective(s) Endpoint(s)		
Primary objective(s)	Endpoint(s) for primary objective(s)	
• To assess the effect of QBW251 compared to placebo after 12 weeks of treatment on fibrinogen plasma concentration.	Change from baseline in fibrinogen plasma concentration.	
Secondary objective(s)	Endpoint(s) for secondary objective(s)	
• Key secondary objective: To assess the effect of QBW251 compared to placebo after 12 weeks of treatment on sputum bacterial load.	 Change from baseline in total bacteria load of colony forming units (CFU/mL) of potentially pathogenic microorganisms in sputum. 	
• Secondary objectives: To assess the effect of QBW251 compared to placebo after 12 weeks of treatment on airway structure and function.	 Change from baseline in airway wall and lumen parameters along with extent of global and regional air trapping, as measured by HRCT. 	
 To assess the effect of QBW251 compared to placebo after 12 weeks of treatment on COPD subjectsubjects symptom burden changes. 	 Change from baseline in COPD Assessment Test (CAT) questionnaire. 	
• To assess the effect of QBW251 compared to placebo after 12 weeks of treatment on health status.	 Changes from baseline in the Euro Quality of Life-5 Dimensions-3 Level (EQ-5D-3L) questionnaire. 	
• To assess the effect of QBW251 compared to placebo after 12 weeks of treatment on changes in health-related quality of life.	 Change from baseline in St. George's Respiratory Questionnaire (SGRQ) total and domain scores. 	
• To assess the effect of QBW251 compared to	Time to first COPD exacerbation	
placebo after 12 weeks of treatment on COPD exacerbations.	 Proportion of subjectsubjects with exacerbations 	
	 Annualized rate of exacerbations as defined by EXACT-PRO questionnaire 	

Novartis	Confidential	Page 7 of 20
SAP Amendment 1		Study No. CQBW251B2202

Objective(s)	Endpoint(s)	
 To assess the effect of QBW251 compared to placebo after 12 weeks of treatment on clinical symptoms, cough and sputum. 	 Change from baseline in Cough and Sputum Assessment Questionnaire (CASA-Q) domain scores. 	
To assess the safety and tolerability of	ECG intervals	
QBW251 in subjects with COPD.	Vital signs	
	 Standard clinical laboratory evaluations (hematology, blood chemistry, and urinalysis) 	
	Adverse events	
 To assess the effect of QBW251 compared to placebo during and after 12 weeks of treatment on pharmacokinetics. 	 Assessment of drug exposure (Ctrough collected at pre-dose and Cmax at post-dose) on Day 1, Day 28, Day 56 and Day 84. Cmax and AUC on Day 1 and Day 28 in subset of subject population (serial 	
	samplings up to 8hr).	
 To assess the effect of QBW251 compared to placebo after 12 weeks of treatment on spirometry. 	Change from baseline in trough FEV1, FVC, and FEV1/FVC.	
Exploratory objective(s)	Endpoint(s) for exploratory objective(s)	

1.4 Study design and treatment

This is a randomized, subject and investigator blinded, parallel-group, placebo-controlled study investigating the mode of action (MoA) and preliminary efficacy and safety of QBW251 administered orally twice daily (b.i.d.) for 12 weeks in subjects with moderate to very severe COPD (GOLD 2-4). Approximately 100 subjects will be randomized in a 1:1 ratio to either QBW251 or placebo. Based on the assumption of a 15% drop-out rate (% drop out based on completed proof-of-concept COPD study CQBW251X2201), it is expected to have approximately 84 subjects to complete the study. Interim analysis plans were discontinued with strategic decision to stop this trial prior to completion.

The study consists of the following periods (Figure 1-1) : Screening, Baseline / Day 1, Treatment, and End of the Study followed by an additional post-treatment safety phone call. The total duration for each subject in the study is up to approximately 19 weeks.

Figure 1-1 Study design

Commercially Confidential Information

Therefore, CQBW251B2202 study drug dose arms are:

- QBW251 CCI
- Placebo b.i.d

2 First interpretable results (FIR)

First interpretable results (FIR) will be provided for this trial. Commercially Confidential Information

3 Interim analyses

Commercially Confidential Information

4 Statistical methods: Analysis sets

For all analysis sets, subjects will be analyzed according to the study treatment(s) received.

No screen failure data will be presented.

The safety analysis set will include all subjects that received any study drug.

The pharmacokinetic (PK) analysis set will include all subjects with at least one available valid (i.e. not flagged for exclusion) PK concentration measurement, who received QBW251 and experienced no protocol deviations with relevant impact on PK data.

The pharmacodynamic (PD) analysis set will include all subjects with PD data at both baseline and at least one post-baseline assessment which are not affected by any protocol deviations.

The analysis sets and protocol deviation codes are related as follows:

Table 4-1		
Category Text description of deviation Deviation code		Data exclusion
Subjects are PDs:	e excluded from Safety analysis in case of these	Exclude subject from Safety analysis set
INCL01	Informed consent was not obtained before any assessment	Y

 Table 4-1
 Protocol deviation codes and analysis sets

Novartis	Confidential	Page 10 of 20
SAP Amendment 1		Study No. CQBW251B2202
Category Deviation code	Text description of deviation	Data exclusion
Subjects are exclu	ded from PK analysis in case of these PDs:	Exclude subject from PK analysis set
INCL01	Informed consent was not obtained before any assessment	Y
TRT04	Subject received incorrect dose	Y
Subjects are exclu	ded from PD analysis in case of these PDs:	Exclude subject from PD analysis sets
INCL01	Informed consent was not obtained before any assessment	Y

If updates to this table are needed, an amendment to the SAP needs to be implemented prior to DBL.

5 Statistical methods for Pharmacokinetic (PK) parameters

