6.1.1 Variables

The primary estimand, defined below, quantifies a hypothetical effect of 12 weeks treatment that would have been observed if all subjects remained on their treatment for 12 weeks:

- **Target population:** subjects with moderate to severe COPD with features of chronic bronchitis and a history of exacerbations and treated with any of the combinations of LABA, LAMA, or ICS LABA/LAMA, LABA/ICS or LABA/LAMA/ICS along with or without macrolides as background therapy.
- Variables of interest: change from baseline in fibrinogen after 12 weeks of treatment.
- Intercurrent events of interest:
 - 1. Discontinuation of study treatment or study participation before 12 weeks of treatment
 - 2. Intake of antibiotics to treat exacerbations (other than macrolides taken as background medication)
 - 3. Intake of systemic corticosteroids to treat exacerbations.
 - 4. Use of rescue medications before 12 weeks of treatment with study drug or placebo is complete
- **Summary measure:** mean difference between treatment groups (QBW251 compared with placebo).

Novartis	Confidential	Page 12 of 20
SAP Amendment 1		Study No. CQBW251B2202

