6.1.3 Statistical model, assumptions and hypotheses

The primary analysis will include all available data from subjects in the PD analysis set.

The fibrinogen samples taken within 2 weeks after exacerbation or during or after last dose of antibiotics other than chronically administered macrolide would be set to missing if a valid unscheduled assessment did not happen at that time point for the primary analysis.

The primary analysis will be performed using a one-sided test at alpha=0.1 (two-sided 80% confidence intervals) and estimated treatment difference (QBW251-Placebo) at week 12 will be reported along with the associated 80% confidence intervals.

The comparison of QBW251 to placebo will be evaluated by testing the following null hypothesis (H_0) versus the alternative hypothesis (H_1) :

H₀: There is no reduction in fibrinogen from baseline after 12 weeks of treatment in

QBW251 compared to placebo.

H1: There is a reduction in fibrinogen from baseline after 12 weeks of treatment in favor

QBW251 compared to placebo.

The change from baseline in fibrinogen data is assumed to be normally distributed. A MMRM will be fitted to the changes from baseline in fibrinogen for all time points until Day 84 visit including the fixed factors and covariates but are not limited to the following:

- Treatment group
- Visit/Time
- Treatment group by time interaction
- Smoking status
- Baseline fibrinogen value by time interaction.

If normality assumptions are not met, then the fibrinogen data may be log transformed.

Sensitivity analyses:

Novartis	Confidential	Page 13 of 20
SAP Amendment 1		Study No. CQBW251B2202

Supportive analyses:

Supportive analyses will be performed on subjects whose fibrinogen levels or bacterial load collected at the visits during the study based on the different baseline treatments like LABA, LAMA, or ICS using repeated measures model similar to primary analyses.

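### The primary fibrinogen comparison groups subjects by treatment received, so a subject given the wrong treatment would change arm or be unclassifiable

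*SAP*

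**What the plan says.** SAP section 4 opens with a rule covering every set: "For all analysis sets, subjects will be analyzed according to the study treatment(s) received". Protocol 12.1 has the same rule. SAP 6.1.3 then states: "The primary analysis will include all available data from subjects in the PD analysis set". The key secondary, bacterial load, uses the same set (protocol 12.5.1, SAP 6.3). The rule therefore decides who counts as QBW251 and who as placebo in the main test.

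The PD set consists of "subjects with PD data at both baseline and at least one post-baseline assessment which are not affected by any protocol deviations". Table 4-1 of the SAP lists the deviations that remove a subject. Receiving an incorrect dose (TRT04) removes a subject from the PK set only; the sole PD entry is missing informed consent (INCL01).

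The primary estimand "quantifies a hypothetical effect of 12 weeks treatment that would have been observed if all subjects remained on their treatment for 12 weeks". Its intercurrent events in the SAP are discontinuation, antibiotics, systemic corticosteroids and rescue medication. Receipt of the wrong treatment is not among them.

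Drug is dispensed at Day 1, Day 28 and Day 56 (protocol Table 8-1). Each time, site staff obtain a medication number from the IRT and hand out the matching kit (protocol 6.7).

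**The concern.** Grouping by treatment received is usual for safety and PK. In a randomised efficacy comparison it lets an event after randomisation decide which arm a subject belongs to. If whatever caused the wrong dispensing is related to fibrinogen outcome, the treatment difference is confounded with it.

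There is also a gap in definition. With three dispensing occasions, one wrong kit among correct ones would leave a subject who has taken both treatments. Neither document says which arm that subject joins, or which record establishes receipt. Protocol 6.4 gives the trial statistician and programmer access to randomisation data, so an ambiguous case could be settled by someone who knows the allocation. At stake is the error rate of the primary test and the traceability of any reclassification.

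**Working it through.** **1. Figures in the plan.** "Approximately 100 subjects will be randomized in a 1:1 ratio to either QBW251 or placebo". "Based on the assumption of a 15% drop-out rate", "it is expected to have approximately 84 subjects to complete the study".

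- Completers: 100 × (1 − 0.15) = 85, against about 84 stated. In reverse, 84 / 0.85 = 98.8, so 99, against about 100. The plan's figure reproduces within rounding, giving 84 / 2 = 42 per arm.
- Alpha: one-sided 0.10 and a two-sided 80% interval share the critical value 1.2816, so the two statements agree.
- Protocol 12.8 (sample size) is redacted, so effect size, SD and power are not available. Effects below are in SD units.

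**2. Weight of one subject.** 1/42 = 2.4% of an arm on completers. The model uses all available data, so the planned denominator lies between 42 and 50, giving 2.0% to 2.4%. This is a share of an arm, not a bias.

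**3. No mismatch.** Treatment received equals treatment assigned for everyone, so the results are identical.

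**4. Mismatches unrelated to prognosis.** Assume 80% power at 42 per arm. The corresponding effect is (1.2816 + 0.8416) × √(2/42) = 0.463 SD. Let m subjects in each arm take the other treatment throughout. Grouping by randomised arm multiplies the expected difference by 1 − 2m/42. Grouping by treatment received leaves it unchanged. With no true effect, simulated type I error by treatment received was 0.099, 0.100 and 0.101 for m = 1, 2 and 4.

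**5. Mismatches related to prognosis (assumed worst case).** A covariate correlates 0.3 with outcome. The m QBW251 subjects with the highest values move to placebo, and the m placebo subjects with the lowest values move to QBW251. There is no true effect, and the test is a simple comparison of two means rather than the full MMRM. In 20,000 simulated trials per setting, the bias by treatment received was −0.060, −0.114 and −0.195 SD for m = 1, 2 and 4. Type I error follows as Φ(−1.2816 + |bias| / √(2/42)), with √(2/42) = 0.218. For m = 1 this is Φ(−1.2816 + 0.275) = 0.157, against 0.158 simulated.

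| Wrong-treatment subjects of 84 (half each way) | Effect retained, by randomised arm | Power, by randomised arm | Power, by treatment received | Worst-case type I, by treatment received | Worst-case type I, by randomised arm |
|---|---|---|---|---|---|
| 0 | 1.00 | 80% | 80% | 0.10 | 0.10 |
| 2 | 0.95 | 77% | 80% | 0.16 | 0.10 |
| 4 | 0.90 | 74% | 80% | 0.22 | 0.10 |
| 8 | 0.81 | 67% | 80% | 0.35 | 0.10 |

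The power columns assume errors unrelated to prognosis (step 4); the type I columns use step 5. The mismatch counts and the correlation are assumptions, because the documents give neither.

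**The case against.** The strongest reply is that this may never matter. The IRT ties each subject to an arm and a medication number (protocol 6.3.2), and capsules, packaging and labelling are identical (6.1.1, 6.4). Mismatches should therefore be few, and selection on prognosis is hard to bring about. That stands, and it limits the size of the point.

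A reader might infer that the plan gives up randomisation for the whole primary comparison. The text does not support this: only subjects whose received and assigned treatments differ are affected. A reader might also infer that the rule brings no benefit. Step 4 shows otherwise: with errors unrelated to prognosis it avoids a 5% to 19% dilution and a power loss of 3 to 13 points for 2 to 8 such subjects. It could be defended in a mode-of-action study declared non-confirmatory (protocol 12), with an estimand framed around staying on treatment. The documents do not offer that defence, and a hypothetical estimand does not call for moving subjects between arms.

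A wrong-kit subject might instead be excluded under the deviation clause in the PD set definition. On Table 4-1 as written, that does not happen, although the table can be amended before database lock. The clause does show that the PD set, selected on post-baseline data and deviations, is already not the full randomised population. Relabelling arms does not cure that.

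Finally, treatment errors are already recorded on the CRF (protocol 10.1.5), and study drug administration is listed by subject (SAP 7.2). The data for a mismatch count therefore exist, but the classification rule does not.

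**Conclusion.** The point holds conditionally. Both documents assign arms in the primary and key secondary analyses by treatment received, without a reason, without a by-randomised analysis in the readable text, and without a rule for subjects who took both treatments. Only grouping by randomised arm guarantees the 10% error rate whatever caused a mismatch.

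The effect is nil with no mismatch. With 2 to 8 mismatches among 84, type I error ranges from about 0.10 (errors unrelated to prognosis) to 0.16–0.35 (assumed worst case, unlikely under blinded IRT supply). These are ranges and do not show that the test is inflated. SAP 1.4 says the trial was stopped before completion, so the achieved number is probably lower and each mismatched subject would weigh more than calculated here.

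Nothing in the documents points to a fault in how smoking status is handled; it is the stratification factor and is in the model. The concern does not extend to it.

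Severity: minor unless mismatches occurred.

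**What to change.** Before database lock, amend SAP section 4 as follows:

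- PD and efficacy analyses, including the primary and key secondary, group subjects by randomised arm.
- Safety and PK analyses keep treatment received, with a stated rule for subjects who received both treatments and a named record that establishes receipt.
- The report gives the number of subjects whose received and assigned treatments differ. If there are any, the as-received result is shown as supportive.

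Align protocol 12.1 only if the protocol is amended for another reason. Under protocol 14.1 an amendment needs sponsor and IRB/IEC approval, and health-authority approval where required, which is out of proportion for this point alone in a trial being stopped.

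The cost is a few sentences in the SAP and no new data. Planned sample size and alpha do not change. The statistical price is the dilution in step 4, about 5% of the effect for 2 of 84 subjects, if mismatches occur and are unrelated to prognosis. The supportive analysis would show the undiluted estimate.

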### Procedural risks

Procedural risks may include:

- Local reactions to venipuncture, including pain, hematomas, fainting, swelling, infections, and erythema.
- Spirometry may be associated with cough, shortness of breath and headache.
- HRCT involves exposure to radiation. The total amount of radiation for acquisition at screening and Week 12 HRCT scans will be optimized to be within the annual limits of exposure defined in both US and EU guidelines.
- Hypertonic saline solution for sputum induction might cause bronchospasm

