# 10.1.3 SAE reporting

To ensure subject safety, every SAE, regardless of causality, occurring after the subject has provided informed consent and until 30 days after the last study visit must be reported to Novartis within 24 hours of learning of its occurrence as described below. Any SAEs experienced after this period should only be reported to Novartis if the investigator suspects a causal relationship to study treatment.

**Screen Failures:** If a subject fails screening (e.g. a subject who is screened but is not treated or randomized), SAEs occurring after the subject has provided informed consent until the time the subject is deemed a Screen Failure must be reported to Novartis.

Randomized Subjects who discontinue prematurely: SAEs collected between the time a subject signs the ICF until 30 days after the subject discontinued or stopped study treatment, or had their last study visit, which ever is later should be reported to Novartis/sponsor safety within 24 hours of learning of its occurrence.

All follow-up information for the SAE including information on complications, progression of the initial SAE and recurrent episodes must be reported as follow-up to the original episode immediately, without undue delay, and under no circumstances later than 24 hours of the investigator receiving the follow-up information. An SAE occurring at a different time interval or otherwise considered completely unrelated to a previously reported one must be reported separately as a new event.

If the SAE is not previously documented in the Investigator's Brochure or Package Insert (new occurrence) and is thought to be related to the study treatment, a Novartis Chief Medical Office and subject Safety (CMO&PS) Department associate may urgently require further information from the investigator for health authority reporting. Novartis may need to issue an Investigator Notification (IN) to inform all investigators involved in any study with the same study treatment that this SAE has been reported.

Suspected Unexpected Serious Adverse Reactions (SUSARs) will be collected and reported to the competent authorities and relevant ethics committees in accordance with EU Guidance 2011/C 172/01 or as per national regulatory requirements in participating countries.

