# 12 Data analysis and statistical methods

The analysis will be conducted on all subject data at the time the trial ends. Any data analysis carried out independently by the investigator should be submitted to Novartis before publication or presentation.

The baseline value is defined as the last assessment prior to first dose administration. In case the scheduled baseline assessment value is missing, the screening value if available will be used instead.

No multiplicity adjustments will be considered due to the non-confirmatory nature of this study.

Screen failure subject's data will not be reported unless an SAE occurs during screening. For SAEs in screening, all subject data will be reported

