## 12.1 Analysis sets

For all analysis sets, subjects will be analyzed according to the study treatment(s) received.

The safety analysis set will include all subjects that received any study treatment.

The PK analysis set will include all subjects with at least one available valid (i.e. not flagged for exclusion) PK concentration measurement, who received any study drug and experienced no protocol deviations with relevant impact on PK data.

The PD analysis set will include all subjects with PD data at both baseline and at least one postbaseline assessment which are not affected by any protocol deviations.

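### SAP section 4 conflicts with the protocol on reporting screen failures who have an SAE, and with the protocol and itself on treated subjects with a consent deviation

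*SAP*

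**What the plan says.** **Screen failures.** Protocol section 12 withholds their data with one exception: "Screen failure subject's data will not be reported unless an SAE occurs during screening". It then sets the extent of reporting: "For SAEs in screening, all subject data will be reported". SAP section 4 reads "No screen failure data will be presented" and stops there.

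**Safety set.** Protocol 12.1 says "The safety analysis set will include all subjects that received any study treatment". SAP section 4 says nearly the same: "The safety analysis set will include all subjects that received any study drug". Table 4-1, in the same SAP section, has a safety block headed "Exclude subject from Safety analysis set" with one entry marked Y. That entry is INCL01, the code for consent not having been in place ahead of any assessment.

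**Use of the set.** SAP section 7 runs every safety analysis on the safety set. SAP 7.2 uses it for the two adverse-event tables required by the public registries. SAP 7.2 also plans listings of all AEs, SAEs and fatal AEs, and a listing of subjects left out of any analysis set with the reason.

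**The concern.** The SAP says in section 1.1 that it implements the analysis planned in the protocol, and section 1.2 cites protocol version 02. It marks neither departure as a change, so a programmer would simply follow it.

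For screen failures, SAEs are nearly all the safety information that exists. A footnote to the protocol's assessment schedule limits other adverse-event collection in screening to exacerbations. Screening also carries some risk. It includes a bronchodilator challenge and may include sputum induction, of which Protocol 4.5 says "Hypertonic saline solution for sputum induction might cause bronchospasm". A screening SAE in a screen failure is foreseeable: exclusion criterion 7 fails a subject hospitalised for an exacerbation in screening, and Protocol 10.1.2 makes hospitalisation a criterion of seriousness.

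For INCL01, what is at stake is a dosed subject disappearing from the exposure, AE, laboratory, vital-sign and ECG summaries because of a consent-timing fault that has no bearing on whether the drug was taken.

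**Working it through.** The plan gives no figure on this point, so the check is a comparison of rules, followed by one calculation for scale.

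**(a) Screen failures**

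1. Collection: Protocol 10.1.3 requires that "SAEs occurring after the subject has provided informed consent until the time the subject is deemed a Screen Failure must be reported to Novartis". The data will therefore exist.
2. Protocol output: a screen failure with a screening SAE has all data reported. Other screen failures have none.
3. SAP output: none for any screen failure.
4. Difference: exactly the screen failures with a screening SAE. A subject who has a screening SAE and is later randomized is not a screen failure under the protocol glossary, so the SAP sentence does not reach that subject.
5. Effect on rates: none. Protocol 12.5.2 and SAP section 7 both restrict AE summary tables to on-treatment events. What is lost is the separate output for these subjects.

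**(b) INCL01**

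1. Protocol 12.1 allows protocol deviations to affect membership of the PK and PD sets. It names no deviation for the safety set.
2. The SAP's sentence defining the safety set also has no exclusion.
3. Table 4-1 excludes the whole subject and does not ask whether the subject was dosed. The SAP therefore conflicts with the protocol and with its own definition.
4. The wording of INCL01 covers two cases: consent given after some assessment had been done, and consent never given. The first can occur in a subject who went on to take the full course of study drug.
5. Because SAP sections 7 and 7.2 tie the summaries and registry tables to the safety set, such a subject leaves all of them.
6. The listing of excluded subjects promises names and reasons, not events. SAP 5.2 says expressly that PK listings keep subjects who are outside the PK set; no matching statement is made for safety.

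**Scale of (b)**

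Inputs: about 100 randomized 1:1 (SAP 1.4), so n = 100/2 = 50 per arm. Assumption: one treated INCL01 subject who had an SAE, in an arm with k subjects with an SAE.

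Change in incidence = k/n − (k−1)/(n−1).

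- k = 1, n = 50: 1/50 − 0/49 = 2.0% − 0% = 2.0 percentage points.
- k = 1, n = 25 (half the planned arm, assumed because SAP 1.4 says the trial was stopped before completion): 1/25 − 0/24 = 4.0 percentage points.

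The documents do not give the number of INCL01 deviations, the number of screening SAEs or the final arm sizes.

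**The case against.** The strongest reply is that little is actually lost. Several parts of it stand.

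- A reader might infer that serious events go unreported. The documents do not support that: Protocol 10.1.3 still sends every SAE to the sponsor within 24 hours, including those of screen failures. The conflict concerns the study report and registry output.
- A reader might infer that all screening SAEs vanish. They do not; only those of screen failures are affected, and no on-treatment rate moves.
- The planned listings of all AEs, SAEs and fatal AEs could be read as covering treated subjects outside the safety set. That is possible, so omission of their events is not certain. Nothing says they are covered, however, and section 7 points the other way.
- Exclusions are already visible, with reasons, in the listing under SAP 7.2.
- Table 4-1 may be a deliberate limit on using data without valid consent. That is a fair reason not to delete the row outright, since deletion would put never-consented subjects into the safety set. It does not justify excluding late consenters, and neither document states such a limit for the safety set.
- Protocol 11.3 requires full verification that consent is present, so treated INCL01 cases may be none.

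Two tempting arguments about screening risk should not be used. Drug washout during screening is not established: exclusion criterion 15 places it before screening, while the title of Table 6-6 refers to Day 1. HRCT is timed late in screening so that subjects who fail are largely spared it (Protocol 8.3.2).

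**Conclusion.** Both conflicts are real and can be read directly from the text. The first drops study-report output that the protocol promises for screen failures with an SAE. The second can remove a dosed subject from every safety-set summary and from the registry tables, with no assurance that the subject's events are listed elsewhere.

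The point is minor. It affects no efficacy conclusion, and its safety effect depends on events that the documents do not show to have occurred. The 2-percentage-point illustration assumes the planned 50 treated per arm and an excluded subject with the only SAE in that arm; one subject would weigh more in smaller arms. The documents do not support a conclusion that serious events are hidden from the sponsor, or that the safety results are biased in either direction.

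**What to change.** 1. In SAP section 4, replace the blanket sentence on screen failures with the protocol's rule: no screen-failure data except for subjects with an SAE during screening, for whom an SAE and subject-data listing is produced.
2. In Table 4-1, limit the INCL01 safety-set exclusion to subjects who never gave valid consent. Keep dosed subjects whose consent was late in the safety set, and record the deviation.
3. State in SAP 7.2 that AEs, SAEs and deaths of any treated subject still excluded are listed separately, as far as data-use rules allow.

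The SAP itself requires changes to Table 4-1 to be made by amendment before database lock, so all three can go into one amendment. The cost is small: two edits to section 4, one sentence in 7.2, and the programming of short listings that may turn out empty. No new data are needed.
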